**Table 1 Analysis population**

	Efficacy	SAF	PP
DEMOGRAPHIC CHARACTERISTICS			
-Baseline characteristics	x	x	x
-Previous treatment	x		
EFFICACY (Primary & secondary endpoints)			
Primary endpoint: -ORR by RECIST in each cohort	x		x
Secondary endpoints: -Evaluate ORR by modified RECIST 1.1 for immune-based therapeutics (iRECIST) in each cohort -Evaluate median duration of response (DOR) by RECIST in each cohort	x		
SAFETY			
Secondary objective: -Evaluate the safety of APX005M alone or in combination with radiation therapy in each cohort -Treatment exposure		x	

	Efficacy	SAF	PP
Exploratory endpoints			
- PFS (by RECIST 1.1 and iRECIST) by cohort - Duration of stable disease by cohort.	x		
Subgroup analysis			
- Subjects receiving steroids during treatment period by cohort. - LDH pre-treatment values above the upper normal range vs. below upper normal range overall and by cohort - Elevated pre-treatment LDH and prior CTLA4 overall and by cohort	x		

## 4. STUDY ENDPOINTS AND DERIVED VARIABLES DEFINITION

### 4.1 General considerations

The following time unit conversion factors will be applied to convert days into weeks, months, or years

**Table 2 Time unit conversion factors**

1 week	7 days
1 month	30.4375 days
1 year	365.25 days

**Study day:** The date on which the first dose of APX005M is administered is considered as Day 1 of the study.

For the events occurring on or after this day, the study day is calculated as the event date minus the date of the first administration of APX005M plus 1 day.

For the events occurring before the start of treatment, study day is calculated as the event date minus the date of the first administration of APX005M.

**Baseline:** is defined as the last non-missing value before treatment.

**On treatment period** is defined as the time elapsed (in months) from the first dose of APX005M and the date of End of Treatment reported at the End of Treatment form.

**Follow up period** is defined as the time elapsed (in months) from the date of the End of Treatment reported at the End of Treatment form and the date of the End of the Study reported at the End of the Study form.

### 4.2 Baseline and Demographics Characteristics

Demographics and baseline characteristics by cohort will be summarized using descriptive statistics.

**Age:**

Is defined as the time elapsed (in years) between the birth date and the informed consent date. This variable is a derived variable that appears in the demographics form.

**Previous diagnosis before the diagnosis of metastatic or advanced disease (Yes/No):**

If the date of the first positive biopsy for the disease is before the diagnosis date of advanced or metastatic disease the subjects will be classified as subjects with previous diagnosis before the diagnosis of metastatic or advanced disease.

**Note:**

If the difference between these dates is less than or equal to one month, the subject will be classified as first diagnosed metastatic or advanced disease.

**Time from the first diagnosis to the diagnosis of advanced or metastatic disease:**

Is defined as the time elapsed (in months) from the date of the first positive biopsy for this disease to the diagnosis date of advanced or metastatic disease.

**Time from the diagnosis of advanced or metastatic disease to informed consent:**

Is defined as the time elapsed (in months) from the date of the diagnosis of advanced or metastatic disease to the informed consent date.

**Any metastatic sites at study entry (Yes/No)**

If the subject has any reported metastases at study entry this variable will take the value 'Yes'.

#### **4.3 Prior and Concomitant medications**

Prior medications: are defined as medications that started and stopped before the first dose of any investigational product.

Concomitant medications: are defined as medication (including all prescription, over the counter, herbal supplements, and IV medications and fluids) that continued or started on or after the first dose of any investigational product, up to 30 days after the last dose of investigational product.

## 4.4 Efficacy Endpoints

For subjects included in Cohort 3, information on the lesions that are radiated will be recorded for follow-up purposes.

These radiated lesions will not be considered in the tumor evaluation of the subjects.

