3.2.2 Radiation Therapy

All subjects should be evaluated and treated by a local radiation oncologist. All radiation treatment will follow the standard guidelines for a SBRT treatment course. Each radiation therapy target lesion will receive up to a total of 3200 cGy in 4 fractions of 800 cGy, administered on the same day and prior to infusion of APX005M. Fractions will be delivered every 2 weeks with the requirement of a minimum of 4 field 3D conformal planning to meet dose constraints to limit normal tissue toxicity of organs at risk (OAR). The first target lesion and the subsequent target lesion will be identified by the treating investigator based upon considerations of clinical benefit and toxicity risk. The RT target lesions shall not be CNS metastases.

First Radiation Therapy Target: One of 3 or more measurable disease lesions (as defined by RECIST 1.1) will be selected as the first radiation therapy target and will be treated every

2 weeks during the first 8 weeks. The radiation field of the first target shall not overlap with any other target lesions.

Second Radiation Therapy Target: The second target shall be one of the remaining non-irradiated lesions where the radiation field does not overlap with the first radiation target. The radiation field shall not overlap with at least one non-irradiated target lesion.

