3.2.2.4.2 Planning Technique

A 3D conformal or IMRT planning technique must be used. If not using IMRT, field edges and MLC blocking must be conformal to the PTV. The dose distributions must include corrections for tissue density heterogeneities. Regardless of planning technique, the dose prescription criteria specified shall be prioritized.

Table 1C: Radiation Dose Criteria

Name of Structure	Dosimetric Parameter	Per Protocol	Variation Acceptable
PTV	Dmin (%)	\geq 90	\geq 85
	D100% (%)	\geq 95	\geq 85
	Dmax (%)	\leq 130	\leq 150

Replanning: Because melanoma can respond robustly to radiation and treatments will be every 2 weeks it is possible that the tumor volume will be considerably smaller for subsequent fractions. It is recommended that response be assessed after two fractions for bigger tumors or

tumors where decrease in size can considerably impact OARs and toxicity risk. If there has been a decrease of tumor volume by more than 2-fold then a new plan should be considered.

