4.1 Procedures by Visits

4.1.1 Screening Period

All patients must provide written informed consent before any study specific assessments or procedures are performed.

The screening assessments should be performed within 21 days before beginning of the Treatment Period. The following study evaluations will be performed during the screening period:

- Collect demographics
- Collect medical history (including concomitant medications)
- Perform physical examination including (including weight, height, and vital signs) and a 12-lead electrocardiogram
- ECOG performance status
- Laboratory evaluations:
 - 1) urinalysis
 - 2) serum chemistry
 - 3) hematology
 - 4) coagulation
- Assess eligibility (inclusion/exclusion criteria)
- Tumor assessment following RECIST 1.1 Guidelines
- Collect archived tumor tissue
- Collect and submit a tumor core biopsy from consenting subjects. Selection of tumor lesions should not interfere with subsequent tumor assessments when feasible
- For Cohort 3: SBRT treatment planning
- Pregnancy test (if applicable)

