4.3 Efficacy Assessments

Tumor assessment will be performed within 21 days prior to start of investigational therapy and during the Treatment Period (every 8 ± 1 week). Subject that discontinue treatment before the first scheduled on study tumor assessment (8 weeks following the first dose of APX005M) should have the tumor response evaluated at the end of treatment visit. Tumor assessments will follow RECIST 1.1 guidelines. Complete or partial responses should be confirmed at a subsequent time point 4 weeks later.

Subjects enrolled in Cohort 3 are required to have a minimum of 3 measurable target lesions. The lesions which are the first and second radiation therapy targets should be recorded.

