6.3 Endpoint Definitions

Endpoint	Description
Primary	
• ORR (rate of CR and PR) by RECIST 1.1 in each cohort
Secondary	
• Incidence and severity of AEs and specific laboratory abnormalities graded according to NCI-CTCAE, v4.03• Changes from baseline of vital signs and clinical laboratory results during and following investigational therapy(ies) administration• ORR (rate of CR and PR) by iRECIST in each cohort• DOR (by RECIST 1.1) by cohort, defined as the time from the first evidence of confirmed PR or better to disease progression or death due to any cause• DOR (by iRECIST) by cohort, defined as the time from the first evidence of confirmed PR or better to disease progression or death due to any cause
Exploratory	
• PFS (by RECIST 1.1) by cohort, defined as time from first dose of investigational therapy(ies) to the earlier of PD or death due to any cause• PFS (by iRECIST) by cohort, defined as time from first dose of investigational therapy(ies) to the earlier of PD or death due to any cause• Association between potential tumor and/or blood biomarkers and antitumor activity and/or resistance to treatment• Presence and titer of anti-APX005M antibodies

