6.4.3 Efficacy Analyses

Tumor assessments by Investigator will follow RECIST 1.1 and iRECIST. ORR (and 90% confidence interval by exact distribution), DOR and PFS (Kaplan-Meier estimate) will be estimated for each cohort and for each tumor assessment method. Additional details will be provided in the Statistical Analysis Plan.

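### SAP 4.4 removes irradiated lesions from all Cohort 3 tumor evaluation without saying how they count for CR or progression, keeps the RECIST 1.1 label, and omits the change from SAP 2.4

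*SAP*

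**What the plan says.** **Protocol.** Section 6.3 gives the primary endpoint as "ORR (rate of CR and PR) by RECIST 1.1 in each cohort". Section 6.4.3 adds: "Tumor assessments by Investigator will follow RECIST 1.1 and iRECIST". Cohort 3 patients need at least three measurable non-CNS target lesions, and up to two are irradiated, one in each 8-week block (sections 2.2 and 3.2.2). On the first field, section 3.2.2 says: "The radiation field of the first target shall not overlap with any other target lesions". On the second: "The radiation field shall not overlap with at least one non-irradiated target lesion". So at least one target lesion is always spared. For response assessment, section 4.3 says only: "The lesions which are the first and second radiation therapy targets should be recorded". Nothing in the protocol takes these lesions out of the response evaluation.

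**SAP.** Section 4.4 opens, above every efficacy endpoint, by saying that irradiated lesions in Cohort 3 are recorded for follow-up, and then: "These radiated lesions will not be considered in the tumor evaluation of the subjects". It makes no exception for CR or for progression. Sections 4.4.2.1 and 5.3.2.1 still call the result ORR by RECIST 1.1 and estimate it for each cohort and overall. Section 2.4, which sets out the changes from the Amendment 2 analyses, covers replacement, populations, disease control rate, clinical progression in DoR and PFS, duration of stable disease and subgroups. It does not mention this rule.

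**The concern.** The rule changes how the primary endpoint is scored in the largest cohort, yet the endpoint keeps its protocol name and the change is not declared where the SAP declares its changes. A reader of the report would take the Cohort 3 figure for an ordinary RECIST 1.1 response rate.

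The wording also reaches further than out-of-field scoring requires. If irradiated lesions play no part in tumor evaluation, their persistence does not block a CR and their growth is not documented progression. The note under SAP Table 4 closes the other route for best overall response, because clinical progression does not count as documented progression there. For DoR and PFS the loss is smaller: SAP 2.4 and Tables 5 to 7 count clinical progression and death as events, so in-field growth can still enter by those two routes, but only by them.

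The overall ORR would combine Cohorts 1 and 2, scored on all lesions, with Cohort 3, scored on some of them.

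**Working it through.** **1. The plan's own figure.** Inputs from protocol 6.1 and SAP 5.1: n = 18, p = 3/18. SE = √(p(1−p)/n) = √(0.1667 × 0.8333 / 18) = 0.0878, which matches the stated 8.8%.

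**2. How a patient is scored under each rule.** Lesion sizes are assumed. RECIST 1.1 is cited but its cut-offs are not printed, so I assume PR at −30% from baseline and PD at +20% with at least 5 mm growth. Each patient has three target lesions, two irradiated and one spared, with no other disease, and any response is taken as confirmed. Change = (later sum / baseline sum) − 1.

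| Case | Baseline, mm (irradiated; spared) | Later, mm | All target lesions | SAP 4.4 read literally |
|---|---|---|---|---|
| A. In-field growth | 30 + 30; 30 | 50 + 40; 20 | 110/90 = +22%, PD | 20/30 = −33%, PR |
| B. In-field disease persists | 30 + 30; 20 | 30 + 30; 0 | 60/80 = −25%, SD | 0/20 = −100%, CR |
| C. In-field shrinkage | 30 + 30; 30 | 10 + 10; 33 | 53/90 = −41%, PR | 33/30 = +10%, SD |

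A and B turn a non-responder into a responder. C does the reverse, and the protocol itself gives a reason to expect cases like C: section 3.2.2.4.2 advises on replanning "Because melanoma can respond robustly to radiation".

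**3. Size per patient.** One patient is 1/18 = 5.6 points. Exact 90% limits are the 5% quantile of Beta(x, n−x+1) and the 95% quantile of Beta(x+1, n−x):

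- 2/18 = 11.1% (2.0–31.0%)
- 3/18 = 16.7% (4.7–37.7%)
- 4/18 = 22.2% (8.0–43.9%)

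This assumes that all 18 planned patients are in the efficacy population.

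**4. Share of the pooled estimate.** 18/(11 + 11 + 18) = 45% of planned patients.

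**5. Timing of the second target.** The second target is irradiated only after the first 8-week block and its tumor assessment (protocol 2.2). The SAP does not say whether that lesion counts at week 8. Suppose the later second target goes from 30 to 36 mm and the spared lesion from 30 to 20 mm. If the later target counts, the week-8 change is 56/60 = −7% (SD). If it is removed, the change is 20/30 = −33% (PR). The protocol gives no date for choosing the second target: section 4.1.1 lists "For Cohort 3: SBRT treatment planning" at screening without saying whether this covers both targets.

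**The case against.** The other side has a good case on several points.

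- **The aim is sound.** Radiation shrinks tumor locally, so scoring lesions outside the field isolates the systemic effect. The field rules in protocol 3.2.2 fit that aim. So does section 3.2.3.4, which requires measurable disease outside the field when non-protocol radiation is considered. Protocol 6.4.3 leaves further detail to the SAP, and the rule is stated openly at the head of SAP 4.4. This stands: the fault is in the breadth of the wording, the label and the omission from section 2.4.
- **A narrower meaning is possible.** The authors may have meant the target-lesion sum only, with RECIST 1.1 otherwise intact. That is not what is written. If it is what was meant, one sentence settles it.
- **The stakes are limited.** The study is exploratory, with no hypothesis test or response threshold. The objective is per cohort, and the pooled ORR already mixes immunotherapy-naive patients with those whose immunotherapy failed. This also stands.

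A reader might infer three stronger things that the documents do not support. The first is that the rule inflates the Cohort 3 ORR; case C shows that it can lower it. The second is that the second target is chosen according to response. No date or rule for that choice is given, and the design figure is not shown in the text, so this is possible but not shown. The third is that the excluded lesions are undefined because the second field may cover further target lesions. The SAP's wording covers lesions that are irradiated, and a lesion inside the field is irradiated on any plain reading.

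**Conclusion.** The concern holds for the SAP as written. Taken literally, section 4.4 produces a response rate for non-irradiated lesions under the name RECIST 1.1 ORR, can record a CR with irradiated disease present, and keeps in-field growth out of progression for best overall response and ORR. The change is missing from section 2.4.

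How many patients are affected, and in which direction on balance, cannot be determined from the documents. In an 18-patient cohort planned around three responders, a single reclassification is a third of the expected responses. The examples rest on assumed lesion sizes and cut-offs and show what the rule permits, not how often it happens. The separate tables, listings and figures document named in SAP section 7 was not available and may settle some details, but a rule that governs the primary endpoint belongs in the SAP. This should be corrected before analysis; it does not invalidate the study.

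**What to change.** 1. **SAP 4.4, scope.** Limit the exclusion to the target-lesion sum. Follow irradiated lesions as non-target lesions, so that CR requires their disappearance and their unequivocal progression counts as PD. This convention is a proposal and is not printed in the documents. Under it, case B would be a PR rather than a CR, and case A would turn on whether the growth is judged unequivocal.
2. **Label and companion estimate.** Call the Cohort 3 result the non-irradiated-lesion ORR. Beside it, report the protocol's RECIST 1.1 ORR on all target lesions where measurements were captured, with the number of patients who have them. Footnote the overall ORR as combining two scoring rules.
3. **Second target.** State whether it counts before it is irradiated, and use the same lesions in the baseline and follow-up sums being compared. Remove it from the baseline and week-8 sums only if it was chosen before the week-8 assessment, since removing it retroactively could let response decide which lesions are scored. Otherwise, report an ORR excluding only the first radiation target as a sensitivity analysis. Keep the second target in for patients who never start the second course.
4. **SAP 2.4.** List the exclusion as a modification.

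**Cost.** Items 2 to 4 are mostly wording and a little programming. Item 1 needs the status of irradiated lesions at each assessment, and the all-target ORR needs their diameters. The documents promise only that these lesions are recorded and that images may be collected (protocol 4.3 and 4.3.1), so the data may be incomplete; if so, the report should say so. Enrollment closed on 21-Oct-2021 (SAP 5.3.8), so the analysis text is where this can be changed. The Cohort 3 ORR may come out slightly less favourable.

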### 4.4.1 Best Overall Response

#### 4.4.1.1 RECIST confirmed Best Overall Response (BOR)

The confirmed Best Overall Response (BOR) is defined as the best response presented according to RECIST v1.1 from the inclusion in the study to documented disease progression. (Only tumor assessments performed before the end of treatment visit date or within 30 days after the administration of the last dose of treatment will be considered in the assessment of BOR).

Partial and complete responses should be confirmed.

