3.3.1 Discontinuation of Subjects from Study

Subjects who are withdrawn from APX005M will enter the Follow-up Period unless study treatment discontinuation is due to any of the following:

- Subject death
- Withdrawal of consent for all study procedures
- Initiation of any anticancer therapy (except for subjects continuing immediately following this study on a PD-1/PD-L1 containing regimen for whom the regimen and the response to that regimen should be documented)
- Subject is lost to follow-up
- Study termination by Apexigen.

Subsequent anticancer regimen should be documented. For subjects, who switch to a PD-1/PD-L1 containing regimen immediately after study treatment the response to that regimen should be documented. Once this information is collected, a subject is considered off-study.

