4.1.3 Follow-up Period

- Follow-up AEs related to APX005M until resolution, stabilization, until improvement is not expected, 30 days, death, or initiation of new anticancer therapy, whichever occurs first
- Record SAEs, pregnancies and AEs with potential immunologic etiology up to 90 days, death, or initiation of new anticancer therapy, whichever occurs first. Follow-up SAEs, pregnancies and AEs with potential immunologic etiology until resolution, stabilization, until improvement is not expected, 90 days from APX005M, death, or initiation of new anticancer therapy, whichever occurs first
- Record ConMeds
- Report date of death or progressive disease
- Record subsequent treatment and date
- For subjects continuing immediately following this study on a PD-1/PD-L1 containing regimen, the regimen and the response to that regimen should be documented.

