##### 3.3.4 Per Protocol population (PP)

The Per Protocol population (PP) is defined as all the subjects of the efficacy population who do not meet one or more of the following criteria that will potentially impact the primary efficacy objective:

- Deviations for the inclusion or exclusion criterion.
- Use of prohibited and/or restricted therapies.
- Patients who have clinical progression without any evidence of pathological or imaging data.

To assess the deviations that may result in the exclusion of subjects from the Per Protocol population, these will be reviewed and approved by the sponsor before database lock for analysis.

The Per Protocol population will be used for sensitivity analysis of the efficacy endpoints and will be considered supportive.

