**Table 4 BOR of NE reasons**

BOR of non-evaluable reasons	BOR
No baseline tumor assessment	NE
No post baseline assessment	NE
All post baseline tumor Assessments have overall response NE.	NE
First tumor assessment with overall response as PD reported after 2 or more missing or NE on treatment tumor assessment (16 weeks or more from the first dose of treatment administered.)	NE

Note:

- Best response could be confirmed during the follow up period.
- Clinical progression /deterioration will not be considered as documented disease progression.

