#### 4.4.4 Duration of Response

##### 4.4.4.1 RECIST Duration of Response (DoR) - Secondary Objective

The Duration of Response (DoR) is defined as the time (in months) from the first evidence of confirmed objective response (CR or PR) to the event or censoring date.

$$DoR \text{ (months)} = \frac{(date \text{ of event or censoring for DoR} - first \text{ date of PR or better}) + 1}{30.4375}$$

An event is defined as the first documentation of progression disease (disease progression assessed based on tumor assessment or clinical progression) or death due to any cause, whichever occurs earlier.

The rules for censoring cases are defined as follows:

If a subject is discontinued or lost to follow up before reporting an event will be censored at the date of the last tumor assessment documenting the absence of PD.

Subjects who start other systemic anti-cancer therapy before an event will be censored at the date of the start of this therapy.

Subjects who die or progress during the follow up period after ≥2 consecutive missed from the last tumor assessment visits will be censored at the date of the last tumor assessment before the tumor assessment of progressive disease or death.

The censoring and event date rules for Duration of Response are presented below.

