**Table 5 Event and censoring dates for DoR analyses**

Events scheme:

Scenario	Date of event
Objective progression.	First date at which progression criteria are met.
Death due to any cause.	Date of death.
Non-objective progression but discontinuation of treatment due to clinical progression.	Date the last tumor assessment before the clinical progression (if any).  In case of not having any tumor assessment, the date of clinical progression should be considered.

Censoring scheme:

Scenario	Date of censoring
PD after 2 or more missed tumor assessments during the follow up period from the last tumor assessment	Date of the last tumor assessment before the event.
No PD and no Death.	Date of last tumor assessment documenting the absence of PD.

Receive any systemic therapy after treatment discontinuation.	Date of last tumor assessment documenting the absence of PD before starting systemic therapy
---	--

DoR analysis will be calculated for subjects with confirmed CR or PR as Best Overall Response.

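### The SAP's best overall response rule does not stop at new anticancer therapy, so a response confirmed only after an immediate PD-1/PD-L1 switch can count in the primary ORR

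*SAP*

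**What the plan says.** **Best overall response.** SAP 4.4.1.1 defines confirmed BOR as the best RECIST 1.1 response between study inclusion and documented progression, and limits the scans used: "Only tumor assessments performed before the end of treatment visit date or within 30 days after the administration of the last dose of treatment". CR and PR need confirmation, and protocol 4.3 gives the interval: "Complete or partial responses should be confirmed at a subsequent time point 4 weeks later". The notes under Table 4 add "Best response could be confirmed during the follow up period" and say that clinical progression does not count as documented progression. New anticancer therapy is not mentioned in 4.4.1.1, in Tables 3 and 4, or in the ORR definition in 4.4.2.1.

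**Time-to-event endpoints.** For DoR, SAP 4.4.4.1 says "Subjects who start other systemic anti-cancer therapy before an event will be censored at the date of the start of this therapy". Table 5 uses a different date, "Date of last tumor assessment documenting the absence of PD before starting systemic therapy", but it too stops at the new therapy. PFS and iPFS (4.4.5.1 and 4.4.5.2, Tables 6 and 7) have matching rules.

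**Follow-up after a switch.** Protocol 3.3.1 lists the events that keep a subject out of follow-up. One is "Initiation of any anticancer therapy (except for subjects continuing immediately following this study on a PD-1/PD-L1 containing regimen", and SAP 2.3.6 repeats the exception. Protocol 4.1.3 adds: "For subjects continuing immediately following this study on a PD-1/PD-L1 containing regimen, the regimen and the response to that regimen should be documented".

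**Per-protocol set.** SAP 3.3.4 removes eligibility deviations, use of prohibited or restricted therapies, and "Patients who have clinical progression without any evidence of pathological or imaging data".

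**The concern.** The primary endpoint has a looser rule on new therapy than the secondary and exploratory endpoints built on the same scans. Starting any other anticancer drug normally ends follow-up and so closes the question. The PD-1/PD-L1 exception keeps it open for the class most likely to produce a response of its own.

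ORR is estimated within each cohort without a control arm, so it is read as the activity of the assigned regimen. If the confirming scan is made on another active drug, the confirmation cannot be credited to that regimen alone. The problem is sharpest in Cohorts 1 and 2, which exclude earlier immunomodulatory agents: PD-1/PD-L1 therapy is a new class for those subjects. It is milder in Cohort 3, where approved immunotherapy has already failed.

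The per-protocol analysis does not reliably remove such a case. Protocol 3.2.3.4 prohibits no therapy during follow-up, so a subject who stops for toxicity or by choice and then switches breaks no rule and stays in that set.

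**Working it through.** **1. The plan's own figures.** Protocol 6.1 and SAP 5.1 assume 2 responders of 11 in each of Cohorts 1 and 2, and 3 of 18 in Cohort 3. With SE = √(p(1 − p)/n):

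- 2/11: √(0.1818 × 0.8182 / 11) = 11.63%, stated as 11.6%.
- 3/18: √(0.1667 × 0.8333 / 18) = 8.78%, stated as 8.8%.

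Both reproduce. The plan has no hypothesis test or power figure to check.

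**2. Effect of one case.** Suppose one of the assumed responders was confirmed only after the switch and is no longer counted. The intervals are exact (Clopper-Pearson) two-sided 90%, as in SAP 5.3.2.1.

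| Cohort | Counted | Not counted | Difference |
|---|---|---|---|
| 1 or 2 | 2/11 = 18.2% (3.3 to 47.0) | 1/11 = 9.1% (0.5 to 36.4) | 1/11 = 9.1 points |
| 3 | 3/18 = 16.7% (4.7 to 37.7) | 2/18 = 11.1% (2.0 to 31.0) | 1/18 = 5.6 points |

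**3. Does the 30-day limit close the gap?** The SAP does not say whether the limit governs the confirming scan or only the first response scan.

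- *Limit does not govern confirmation.* The note under Table 4 then allows confirmation in follow-up with no limit on time or therapy.
- *Limit governs confirmation.* Count days from last dose. Let the first CR/PR scan fall on day p, the confirming scan on day p + 28, and the switch on day s. The confirming scan is on the new drug and still eligible when s < p + 28 ≤ 30. The documents give no switch date, so assume the switch occurs when the next dose would be due:
  - Cohort 1, s = 21: p runs from −6 to +2.
  - Cohorts 2 and 3, s = 14: p runs from −13 to +2.

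  In whole days the window is 30 − s days wide: 9 days for s = 21, 16 days for s = 14, and none once s reaches 30.

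**4. Consistency with DoR.** SAP 4.4.4.1 computes DoR for confirmed responders as (end date − first response date + 1)/30.4375 months. Take a subject whose first CR/PR scan is the last scan before the switch.

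- Table 5 rule (last scan before the new therapy): (0 + 1)/30.4375 = 0.03 months, i.e. 1 day, censored.
- Text rule (start of the new therapy), with that scan on the day of last dose: (21 + 1)/30.4375 = 0.72 months in Cohort 1, or (14 + 1)/30.4375 = 0.49 months in Cohorts 2 and 3.

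Under either rule, the scan that makes the subject a confirmed responder comes after the subject's DoR has been censored.

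**The case against.** The strongest reply is that the route is narrow.

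- The limiting sentence sits inside the definition of confirmed BOR, so it can fairly be read as covering confirmation. The follow-up note then means only that a scan can fall after end of treatment and still be within 30 days of last dose. This is a reasonable reading, but the calculation above shows that it leaves part of the gap open.
- The case needs an unconfirmed CR or PR, a stop without documented progression, an immediate PD-1/PD-L1 switch, and scans at particular times. The switch day is an assumption, and a later switch shrinks the window. All of this stands, and it limits how many subjects could be affected.
- No imaging is scheduled in follow-up (protocol 4.1.3 and Appendix A). A confirming scan would come from the 4-week confirmation request, from routine imaging, or from the recorded response to the new regimen. The wording treats that response as belonging to the next regimen. This is fair, but the SAP nowhere says such a scan may not confirm an earlier response.
- Censoring a time-to-event endpoint and setting a response window are different rules, and the response did first appear on study treatment. That softens the contrast with DoR but does not settle whether confirmation on another drug should count.
- The study is exploratory with no decision threshold, the intervals overlap heavily, and any single misclassified subject would move ORR as much. By-subject response listings are planned, so a case could be found. These points bear on severity. They do not supply the missing rule.

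**Conclusion.** The concern holds. As written, the SAP can credit a response to the primary ORR when its confirming scan was made on another active drug, and nothing else in the protocol or SAP prevents it. One case would be worth 9.1 points in Cohort 1 or 2 and 5.6 points in Cohort 3, which is half and one third of the responders assumed at planning.

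These sizes are illustrative. They assume the planned numbers of 11 and 18 and exactly one affected subject; with none, no result changes. The timing windows also assume a switch when the next dose is due and confirmation at exactly 28 days. The point is worth considering but is not critical, and confidence in its practical weight is medium. The rule is best set before database lock, so that it is not settled case by case in small open-label cohorts.

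**What to change.** Add to SAP 4.4.1.1, before database lock: tumor assessments made after the first dose of any non-protocol systemic anticancer therapy do not count toward CR or PR or toward its confirmation; a scan on the same day but before that dose may count. The subject stays in the denominator as a non-responder unless the response was already confirmed. List every response left unconfirmed for this reason.

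Two details should be settled with it:

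- State whether such a subject's BOR is SD or NE. Table 3 has no row for a CR or PR with no later eligible scan. The choice affects BOR and DCR but not ORR.
- A matching sentence in 4.4.1.2 is optional, because iBOR already ends at end of treatment.

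The cost is one SAP sentence, one listing and one programming condition on the subsequent-treatment date already collected under protocol 4.1.3. No protocol amendment is needed. The downside is that a true APX005M response that could be confirmed only after the switch is not counted, so ORR may be slightly lower; the listing keeps it visible.
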